8.3.1.2 Method of Detecting AE and SAE

Care will be taken not to introduce bias when detecting AE and/or SAE. Open-ended and non-leading verbal questioning of the subject is the preferred method to inquire about AE occurrence.

8.3.1.3 Follow-up of AE and SAE

After the initial AE/SAE report, the investigator is required to proactively follow each subject at subsequent visits/contacts. All SAEs and immune-related AEs will be followed until resolution, stabilization, until the event is otherwise explained, or the subject is lost to follow-up (as defined in [Section 7.1](#)). Further information on follow-up procedures is given in [Appendix 4](#).

8.3.1.4 Regulatory Reporting Requirements for SAE

- Prompt notification by the investigator to the sponsor of an SAE is essential so that legal obligations and ethical responsibilities towards the safety of subjects and the safety of a study treatment under clinical investigation are met.
- The sponsor has a legal responsibility to notify both the local regulatory authority and other regulatory agencies about the safety of a study treatment under clinical investigation. The sponsor will comply with country-specific regulatory requirements relating to safety reporting to the regulatory authority, IRB/IEC, and investigators.
- Investigator safety reports must be prepared for suspected unexpected serious adverse reactions according to local regulatory requirements and sponsor policy and forwarded to investigators as necessary.
- An investigator who receives an investigator safety report describing an SAE or other specific safety information (eg, summary or listing of SAE) from the sponsor will file it along with the Investigator's Brochure and will notify the IRB/IEC, if appropriate according to local requirements.

8.3.2. Pregnancy

- Details of all pregnancies in female subjects and, if indicated, female partners of male subjects will be collected after the start of study treatment and until the pregnancy outcome is known.
- If a pregnancy is reported, the investigator should inform sponsor within 24 hours of learning of the pregnancy.
- Abnormal pregnancy outcomes (eg, spontaneous abortion, fetal death, stillbirth, congenital anomalies, ectopic pregnancy) are considered SAEs.

8.3.3. Physical Examinations

- A complete physical examination will include, at a minimum, assessments of the cardiovascular, respiratory, gastrointestinal and neurological systems. Height and weight will also be measured and recorded.
- A symptom-driven physical examination will focus on the evaluation of the subject's reported signs and symptoms.
- Investigators should pay special attention to clinical signs related to previous serious illnesses.

8.3.4. Vital Signs

- Temperature, pulse rate, respiratory rate, and blood pressure will be assessed.
- Blood pressure and pulse measurements will be assessed with a completely automated device. Manual techniques will be used only if an automated device is not available.
- Blood pressure and pulse measurements should be preceded by at least 5 minutes of rest for the subject in a quiet setting without distractions (eg, television, cell phones).
- Vital signs will be measured in a semi-supine position after 5 minutes rest and will include temperature, systolic and diastolic blood pressure, pulse, and respiratory rate.
- For etigilimab infusions:
 - For first infusion measure vital signs within 60 minutes before infusion, every 15 (± 5 minutes) during the infusion and 30 (± 10 min) and 90 (± 15) minutes after the end of the infusion.

- For subsequent infusions, measure vital signs within 60 minutes before infusion, during infusion if clinically indicated and 30 (± 10) minutes after the end of the etigilimab infusion.
- For nivolumab infusions vital signs should be taken per institutional guidelines.

8.3.5. **Electrocardiograms**

- 12-lead ECG will be obtained as outlined in the SoA (see [Section 8.1](#)) using an ECG machine that automatically calculates the heart rate and measures pulse rate, QRS, QT, and corrected QT intervals.

8.3.6. **Clinical Safety Laboratory Assessments**

- Refer to [Appendix 2](#) for the list of clinical laboratory tests to be performed and to the SoA for the timing and frequency.
- The investigator must review the laboratory report, document this review, and record any clinically relevant changes occurring during the study in the AE section of the CRF. The laboratory reports must be filed with the source documents. Clinically significant abnormal laboratory findings are those which are not associated with the underlying disease, unless judged by the investigator to be more severe than expected for the subject's condition.
- All laboratory tests with values considered clinically significantly abnormal during participation in the study or within 30 days after the last dose of study treatment should be repeated until the values return to normal or baseline. If such values do not return to normal/baseline within a period of time judged reasonable by the investigator, the etiology should be identified, and the sponsor notified.
- All protocol-required laboratory assessments, as defined in [Appendix 2](#), must be conducted in accordance with the laboratory manual and the SoA.
- If laboratory values from non-protocol specified laboratory assessments performed at the institution's local laboratory require a change in subject management or are considered clinically significant by the investigator (eg, SAE or AE or dose hold), then the results must be recorded in the CRF.

8.3.7. **Immunogenicity Assessments**

Antibodies to etigilimab will be evaluated in serum samples collected from all subjects according to the SoA. Additionally, serum samples should also be collected at the final visit from subjects who discontinued study treatment or were withdrawn from the study. These samples will be tested by the sponsor or sponsor's designee.

Serum samples will be screened for antibodies binding to etigilimab and the titer of confirmed positive samples will be reported. Other analyses may be performed to verify the stability of antibodies to etigilimab and/or further characterize the immunogenicity of etigilimab.

The detection and characterization of antibodies to etigilimab will be performed using a validated assay method by a lab vendor under the supervision of the sponsor. All samples collected for detection of antibodies to study treatment will also be evaluated for etigilimab serum concentration to enable interpretation of the antibody data. Antibodies may be further

characterized and/or evaluated for their ability to neutralize the activity of the study treatment(s).

Samples may be stored for a maximum of 1 year following the last subject's last visit for the study at a facility selected by the sponsor to enable further analysis of immune responses to etigilimab.

8.4. Pharmacokinetics

- Blood samples will be collected for measurement of serum concentrations of etigilimab as specified in [Table 3](#). Other samples may be collected at additional timepoints during the study if warranted and agreed upon between the investigator and the sponsor. Instructions for the collection and handling of biological samples will be provided by the sponsor in the laboratory manual. The actual date and time (24-hour clock time) of each sample will be recorded.
- Genetic analyses will not be performed on these blood or serum samples. Subject confidentiality will be maintained. At visits during which samples for the determination of serum concentration of etigilimab will be taken, 1 blood draw of sufficient volume can be used.

8.5. Pharmacogenomics

A 6-mL blood sample for DNA isolation will be collected from subjects who have consented to participate in the pharmacogenomics component of the study. Participation is optional. Subjects who do not wish to participate in the genetic research may still participate in the study.

DNA samples may be used for research related to etigilimab and nivolumab. Pharmacogenomic research may consist of the analysis of 1 or more candidate genes or the analysis of genetic markers throughout the genome (as appropriate) in relation to etigilimab and nivolumab or oncology clinical endpoints.

The final disposition of samples will be conducted per local regulations. Details on processes for collection and shipment of these samples can be found in the Laboratory Manual.

8.6. Biomarkers and Biopsies

Blood and tumor samples will be obtained for biomarker evaluation from all eligible subjects prior to treatment and on treatment as detailed in the SoA. Samples will be processed for the determination of changes in signaling markers downstream of the TIGIT-PVR/PVRL2 axis, Tregs, and potential predictive biomarkers.

Blood biomarkers: A predose sample of 33 mL will be drawn at screening, on Study Days 1, 8, 22, and 36, every 6 weeks after Day 36 for subjects continuing on study drug, and at treatment termination to evaluate changes in plasma proteins eg, IL17, IL2, IFN γ , etc., TIGIT and immune-related gene expression and possible T-cell clonality by mRNA detection (eg, CD226, T-cell genes) and changes in peripheral blood mononuclear cell populations (PBMCs) and activation by flow cytometry.

Tumor tissue: Tumor tissue is required for enrollment. If archival formalin-fixed, paraffin-embedded (FFPE) tumor tissue has not been collected preferably within 6 months of

screening, but no longer than 1 year, or is not available, either fresh core or punch needle biopsy is required at study entry (3 fresh cores/punches preferred whenever possible).

Pre-treatment biopsy: Baseline tumor tissue samples consisting of core needle biopsies of deep tumor tissue or lymph nodes or excisional, incisional, punch, or forceps biopsies of cutaneous, subcutaneous, or mucosal lesions will be obtained for all subjects. Subjects undergoing core needle biopsy should have accessible lesion(s) that permit a total of at least 2 biopsies (pretreatment and on-treatment) without unacceptable risk of major procedural complication (one pretreatment and an optional one on-treatment biopsy will be performed; minimum diameter, 18 gauge). If possible, at least 3 cores will be collected. One or 2 cores will be shipped to central laboratory formalin fixed in ethanol and an additional core will be fresh frozen.

On-treatment biopsy: An optional subsequent biopsy will be performed if the subject consents to the procedure. The biopsy will be performed approximately 8 weeks (\pm 5 days) following the first administration of etigilimab if not medically contraindicated. In the event that the second biopsy cannot be performed approximately 8 weeks after the first administration of etigilimab, the Medical Monitor should be notified to discuss alternative timing for the second biopsy. An additional biopsy may be collected per investigator discretion, preferably at the time of radiographic progression or response. If possible, at least 3 cores will be collected. One or 2 cores will be shipped to central lab formalin fixed in ethanol and an additional core will be fresh frozen.

Requirements and procedures for pre-treatment and on-treatment biopsy collection are identical. The expression of TIGIT, PVR, PVRL2, FOXP3 and other immune markers (eg, protein and/or RNA) may be assessed in tumor specimens. The expression levels of additional proteins and genes (eg, immune gene signatures) may be evaluated and correlated with clinical benefit. Additionally, DNA testing (eg, TMB, mismatch repair genes, TIGIT pathway related genes etc.) of the tumor tissue may be performed on subjects using the tumor specimens collected.

Cell-free DNA: A 10 mL blood sample for cell-free tumor DNA assessments will be collected pre-dose on Study Day 1, Day 36, Day 78 and treatment termination. Analysis of genes relevant to TIGIT, disease genes, mutation burden, and mismatch repair etc. may be performed.

8.7. Skin Biopsy

If a skin rash occurs during study treatment, an optional biopsy and pictures of the skin rash will be performed. The expression of immune infiltrate may be assessed by hematoxylin and eosin staining and/or IHC.

8.8. Deviation Reporting

The following protocol deviations will be recorded and summarized in the final report:

- 1) enrollment violations, 2) dosing violations, 3) concomitant therapy violations, and 4) continuation of therapy when treatment should have been discontinued.

[figure not shown]
9. STATISTICAL CONSIDERATIONS

Data collected in this study will be presented descriptively using summary tables, figures, and data listings. Continuous variables will be summarized using mean, standard deviation, median, minimum, and maximum. Categorical variables will be summarized using counts and percentages. Missing values will not be imputed unless otherwise stated.

9.1. Sample Size Determination

This is a Phase 1b/2 open-label basket study of etigilimab (MPH313) (█ mg dose for subjects \geq 50 kg, █ mg/kg dose for subjects $<$ 50 kg) IV administered Q2W with nivolumab 240 mg Q2W to evaluate preliminary anti-tumor activity, safety and tolerability, PK parameters, immunogenicity, and biomarkers in up to 9 cohorts of subjects with endometrial carcinoma, HNSCC, cervical cancer, ovarian cancer, gastric cancer and gastroesophageal junction adenocarcinoma, TMB-H/MSS cancer, sarcoma, germ cell tumors, and uveal melanoma. Each cohort will be evaluated using a Simon Two-Stage design appropriate to the clinically meaningful response rate for the indication as depicted in [Figure 5](#) below. Interim futility monitoring for each individual cohort using the clinically meaningful response rate criteria per cohort will be carried out in accordance with the optimal Simon Two-Stage design when up to 10 subjects have sufficient data (either discontinued study drug treatment or having at least one post-baseline imaging assessment) for ORR and DoR evaluation by RECIST v1.1. For each cohort, the second stage may be opened for enrollment only after discussion with the IDMC and the sponsor. The sponsor may have an independent assessment of responses to verify investigator-reported responses. The responses based on independent assessments, if available, will be used for sensitivity analysis with sponsor and will make recommendations regarding study conduct, including whether to continue, modify, or stop the study.

Figure 5 **Simon Two-stage Study Design**

Abbreviations: CC = cervical cancer; EC = endometrial cancer; GC = gastric cancer and gastroesophageal junction adenocarcinoma; GCT = germ cell tumors; HNSCC = head and neck squamous cell carcinoma; OC = ovarian cancer; SR = sarcoma; TMB-H = tumor mutational burden-high; UM = uveal melanoma

Type 1 Cohort

The null hypothesis that the true response rate is 0.05 will be tested against a one-sided alternative that the true response rate is at least 0.2. In the first stage, 10 subjects will be enrolled and enrollment in this cohort will be halted until the response data are mature. If there are fewer than 1 responder in these 10 subjects, further enrollment in the cohort may be stopped after review of efficacy and safety data, and discussion by Sponsor with the IDMC. Otherwise, once 1 or more responders in stage 1 are observed, 19 additional subjects may be enrolled for a total of 29. The null hypothesis will be rejected and the treatment will be declared effective and worthy of further testing if 4 or more responders are observed in 29 subjects. This design yields a type I error rate of 0.0468 and power of 80.11% when the true response rate is 0.2.

Type 2 Cohort

The null hypothesis that the true response rate is 0.1 will be tested against a one-sided alternative that the true response rate is at least 0.3. In the first stage, 10 subjects will be enrolled and enrollment in this cohort will be halted until the response data are mature. If there are fewer than 2 responders in these 10 subjects, enrollment in the cohort may be stopped after review of efficacy and safety data, and discussion by Sponsor with the IDMC. Otherwise, once 2 or more responders in stage 1 are observed, 19 additional subjects may be enrolled for a total of 29. The null hypothesis will be rejected and the treatment will be declared effective and worthy of further testing if 6 or more responders are observed in 29 subjects. This design yields a type I error rate of 0.0471 and power of 80.51% when the true response rate is 0.3.

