DLBC	Lymphoid Neoplasm Diffuse Large B-cell Lymphoma	0.49
GBM	Glioblastoma multiforme	0.46
LIHC	Liver hepatocellular carcinoma	0.46
CHOL	Cholangio carcinoma	0.34
LGG	Brain Lower Grade Glioma	0.3
LAML	Acute Myeloid Leukemia	0.076
THYM	Thymoma	0.047

Abbreviations: PD-1 = programmed death-1; TCGA = The Cancer Genome Atlas; TIGIT = T-cell immunoreceptor with Ig and ITIM domains

Legend: TIGIT and PD1 expression in TCGA. Tumor ranked by R value; tumors with correlation greater than R=.7 are shaded.

The purpose of the study is to determine preliminary clinical activity of this combination in several selected tumor groups and identify which subject characteristics, based on histology, biomarker or prior therapy are most like to benefit from this combination.

This open-label basket study trial design is the most effective to evaluate pan tumor safety and clinical activity by histology, TIGIT, and PD-L1 status.

Subject selected for evaluation in this study all have advanced or metastatic disease, who are not candidates for available, curative standard of care therapies, with cancer types considered as high unmet therapeutic need indications for which limited therapeutic options exist. [Table 1](#) illustrates

the historic objective response rate (ORR) for monotherapy with anti-PD-1/anti-PD-L1 antibodies in the tumor types included in this study.

Table 1 Historical ORR with CPI monotherapy for Treatment Cohorts

Tumor Type	ORR for Single Agent CPI
PD-L1 Positive tumors	
Advanced and/or recurrent or metastatic squamous cell carcinoma of the head and neck or for the first-line treatment of subjects with metastatic or with unresectable, recurrent head and neck squamous cell carcinoma (HNSCC)	14%-18%
Recurrent or metastatic cervical cancer with disease progression on or after chemotherapy whose tumors express PD-L1	14% (Chung et al 2019)
Recurrent locally advanced or metastatic gastric or gastroesophageal junction adenocarcinoma with disease progression on or after 2 or more prior lines of therapy including fluoropyrimidine- and platinum-containing chemotherapy and if appropriate, HER2/neu-targeted therapy.	16%-22%
TMB-H	
Advanced or metastatic TMB-H and MSS solid tumors, that have progressed following prior treatment and who have no satisfactory alternative treatment options.	28%
Independent of PD-L1 Status	

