Advanced and/or metastatic endometrial carcinoma, who have disease progression following prior systemic therapy and are not candidates for curative surgery or radiation	23% ~ 40%
Histologically confirmed high grade serous and endometrioid recurrent ovarian cancer, fallopian tube cancer or primary peritoneal cancer following platinum-based front-line regimen per standard of care after primary or interval debulking surgery with documented radiological recurrence.	~10% (Matulonis et al 2020)
Rare disease with high prevalence of TIGIT expression	
• germ cell tumors	0%-15%
• sarcoma	0%-15%
• uveal melanoma	0%-15%

[Schmidt et al 2020](#)

Abbreviations: CPI = checkpoint inhibitor; MSS = microsatellite stable; ORR = overall response rate; PD-L1 = programmed death ligand-1; TIGIT = T-cell immunoreceptor with Ig and ITIM domains; TMB-H = tumor mutational burden-high

This ORR together with the DoR is expected to inform future studies of this combination depending on tumor type.

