4. INTRODUCTION

This statistical analysis plan (SAP) explains in detail the statistical analyses that will be performed for the Mereo Biopharma MPH313-1-02 study. The analysis is outlined within the study protocol V4.0, dated 29 June 2022 and this SAP contains a more technical and detailed description of those analyses outlined in the protocol. In particular, information is provided on the definitions of the study populations, and it also details the list of Tables, Figures and Listings (TFL) that will be produced by S-cubed Biometrics for use and inclusion with the Clinical Study Report (CSR). This SAP provides a detailed description of the analyses that will be undertaken and has been written and finalised before locking the database for the final analysis.

A Data Review Meeting (DRM) will be conducted when the study is complete and data is cleaned, prior to final database lock.

Any deviations from the protocol specified analyses will be listed in Section 11 and any deviations from the analyses stated within this SAP, will be described within the CSR.

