10.1.3. Statistical Testing and Estimation

No formal statistical hypothesis testing will be performed.

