Eastern Cooperative Oncology Group (ECOG) Performance is rated from Grade 0 to Grade 5, as per the table below. ECOG performance status will be summarised as a shift from the status at baseline and will also be listed.

10.11.6. *12-Lead ECG*

ECGs will be carried out at screening, 30 mins post-infusion on Cycle 1 Day 1, 30 mins post-infusion on Cycle 4 Day 1 and at treatment termination. Baseline will be the last non-missing results observed prior to infusion on Cycle 1 Day 1.

Summary statistics for absolute values and change from baseline by scheduled time point will be tabulated, by cohort and for all subjects, for ECG parameters (PR interval, QRS duration, QTc interval (sec) and QTcF interval (sec)).

10.11.7. *Contrast Enhanced Head CT or MRI Scan*

Any data collected for this test will be listed.

11.CHANGES TO THE PROTOCOL SPECIFIED ANALYSIS DETAILED IN THE STATISTICAL ANALYSIS PLAN

An additional definition of Treatment Emergent Adverse Event was added to the SAP:

Any adverse event that occurs after first dose of study treatment and within 100 days of last dose of study treatment regardless of whether they receive any subsequent cancer treatment between last dose of study drug and the adverse event.

Toxicity grades of laboratory parameters are not summarised.

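### Meeting 4/29 or 6/29 rejects only a 5% or 10% ORR, so in five tumor groups it cannot show activity beyond checkpoint-inhibitor monotherapy; SAP 8 also keeps a test that SAP 10.1.3 drops

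*Protocol*

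**What the plan says.** Protocol 9.1 sets two Simon two-stage rules. For a Type 1 cohort (null 5%, alternative 20%), at least 1 responder in 10 opens the second stage, and "the treatment will be declared effective and worthy of further testing if 4 or more responders are observed in 29 subjects". For a Type 2 cohort (null 10%, alternative 30%), at least 2 in 10 opens it, and "the treatment will be declared effective and worthy of further testing if 6 or more responders are observed in 29 subjects". The stated type I error and power are 0.0468 and 80.11% for Type 1, and 0.0471 and 80.51% for Type 2. The synopsis (protocol Appendix 9) and SAP 8 repeat both rules, including the statement that the null is rejected. The figure that assigns cohorts to types is not shown in the available text.

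Protocol 1.3 assigns nivolumab with etigilimab to all subjects. Protocol 1.4.1, Table 1, lists historical ORR for checkpoint-inhibitor monotherapy:

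- head and neck 14-18%
- cervical ("Recurrent or metastatic cervical cancer with disease progression on or after chemotherapy whose tumors express PD-L1") 14%
- gastric 16-22%
- TMB-H/MSS ("Advanced or metastatic TMB-H and MSS solid tumors, that have progressed following prior treatment and who have no satisfactory alternative treatment options") 28%
- endometrial ("Advanced and/or metastatic endometrial carcinoma, who have disease progression following prior systemic therapy and are not candidates for curative surgery or radiation") 23-40%
- ovarian about 10%
- each rare tumor 0-15%

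On the analysis side, SAP 10.1.3 says "No formal statistical hypothesis testing will be performed". SAP 4 says "Any deviations from the protocol specified analyses will be listed in Section 11". SAP 11 has two entries. One begins "An additional definition of Treatment Emergent Adverse Event was added to the SAP"; the other says that laboratory toxicity grades are not summarised.

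**The concern.** The rule attaches the word effective to a result that excludes only a 5% or 10% response rate. In five tumor groups Table 1 expects nivolumab-class treatment alone to exceed both figures. A cohort in which etigilimab added nothing could then be reported as effective, although protocol 1.4.1 wants the ORR to guide later studies of this combination. Cervical cancer is a live case: SAP 6.3 says its stage 1 evaluation took place and approval was given to proceed.

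The second issue is consistency within the SAP. A reader of SAP 8 expects a test of the primary endpoint; a reader of SAP 10.1.3 expects none. SAP 11, where the difference should be explained, is silent.

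**Working it through.** **Inputs.** Stage sizes, cut-offs and nulls come from protocol 9.1, and monotherapy rates from protocol Table 1. Because the assignment of cohorts to types is not visible, both rules are evaluated at each rate.

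**Formula.** Let X1 ~ Bin(10, p) and X2 ~ Bin(19, p), independent, with total X ~ Bin(29, p). The rule is met when stage 1 passes and the total reaches the cut-off:

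- Type 1: P(X ≥ 4) − P(X1 = 0)·P(X2 ≥ 4)
- Type 2: P(X ≥ 6) − P(X1 = 0)·P(X2 ≥ 6) − P(X1 = 1)·P(X2 ≥ 5)

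**Reproducing the plan's figures.**

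- Type 1, p = .05: .05475 − .59874 × .01324 = .0468
- Type 1, p = .20: .85962 − .10737 × .54491 = .8011
- Type 2, p = .10: .06372 − .34868 × .00859 − .38742 × .03519 = .0471
- Type 2, p = .30: .90682 − .02825 × .52614 − .12106 × .71778 = .8051

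All four agree with protocol 9.1, so the design arithmetic is sound.

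**The same rules at the Table 1 rates.** For cervical (p = .14):

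- Type 1: .59365 − .22130 × .27079 = .534
- Type 2: .21233 − .22130 × .04007 − .36026 × .11578 = .162

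Probability of meeting the rule at n = 29 if the combination only matches monotherapy:

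| Tumor group | Table 1 ORR | Type 1 rule | Type 2 rule |
|---|---|---|---|
| Cervical | 14% | .53 | .16 |
| Head and neck | 14-18% | .53-.73 | .16-.34 |
| Gastric | 16-22% | .64-.86 | .24-.52 |
| Endometrial | 23-40% | .88-.99 | .57-.95 |
| TMB-H/MSS | 28% | .95 | .75 |

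These are rejection probabilities at rates above the null, not corrected type I errors.

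**The cut-offs as observed rates.** 4/29 = 13.8%, just under the cervical 14%. 6/29 = 20.7%, above the cervical rate but below the TMB-H and endometrial rates.

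**The SAP sections side by side.** SAP 8 carries over the protocol's statement that the null is rejected at the cut-off. SAP 10.1.3 rules out formal testing. SAP 4 sends departures from the protocol's analyses to SAP 11. Neither entry in SAP 11 concerns the primary endpoint.

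**The case against.** The best defense is that the label has little consequence. The objective is a preliminary assessment, the phrase also says only that further testing is warranted, Table 1 sits in the same protocol, and no planned table prints the label. Cohort D recruited nobody, and Cohort B has no response-evaluable subjects. The study was terminated, and protocol 1.3 and SAP 6.1 plan at most 20 subjects per cohort, so 29 may never have been reached. All of this stands and lowers the weight. It does not make the sentence correct.

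The missing figure also matters. For cervical cancer the probability is .53 under one rule and .16 under the other, and the closeness of 13.8% to 14% counts only if that cohort is Type 1.

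On the SAP conflict, protocol 9, 9.3 and 9.3.1 already plan descriptive summaries and an exact 95% CI for ORR. SAP 10.1.3 therefore agrees with the protocol's analysis section and departs only from the decision rule in 9.1. A reader might infer that a planned primary analysis was quietly abandoned. The documents support only an unreconciled sentence.

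A reader might also infer that the rule says nothing about monotherapy in any cohort. That goes too far. The Type 2 null equals the ovarian rate of about 10%, and both nulls lie within the rare-tumor range of 0-15%. For subjects already treated with a checkpoint inhibitor (Cohort G, and some of B, D and E), Table 1 gives no rate to compare with.

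**Conclusion.** The point holds in limited form, and its weight is minor. For checkpoint-naive subjects with head and neck, cervical, gastric, TMB-H/MSS or endometrial tumors, meeting 4/29 or 6/29 shows an ORR above 5% or 10% and no more. In the cohorts where this can still matter, a combination equal to monotherapy would meet the rule with probability .53/.16 (cervical), .95/.75 (TMB-H) or .88-.99/.57-.95 (endometrial) under Type 1/Type 2. No claim is made for ovarian cancer, the rare tumors or pretreated subjects.

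The stated 4.7% errors should not be read as wrong. They reproduce exactly and answer the question posed by the 5% and 10% nulls.

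The probabilities assume that Table 1's class-wide anti-PD-1/PD-L1 rates stand in for nivolumab, that stage 1 stopping is applied, and that the cohort reaches 29. Stopping is worded as optional; without it the cervical figures rise to .59/.21.

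Separately, SAP 8 and SAP 10.1.3 conflict, and SAP 11 omits an entry that SAP 4 promises. That finding needs no assumption.

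**What to change.** 1. In protocol 9.1, the synopsis and SAP 8, drop the claim of effectiveness so that the label reads *considered worthy of further testing*. Add that the cut-offs reject only a 5% or 10% ORR and, for the five tumor groups above, do not show activity beyond checkpoint-inhibitor monotherapy.
2. In SAP 8, state that the Simon rule is kept only as the basis for sample size and futility monitoring, consistent with SAP 10.1.3.
3. In SAP 11, list that the final test in protocol 9.1 will not be performed.

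If the protocol is no longer being amended, SAP 8 and SAP 11 can carry the change.

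Sample size, cut-offs, error rates and tables stay as they are. The cost is a few sentences and a narrower claim.

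I would not add the Table 1 rates as a reference row in Table 14.2.1. Cohort E would need a separate interval for checkpoint-naive subjects, which SAP 10.1.6 excludes. The endometrial reference is a range, so whether an interval contains it is undefined. The rates are cross-trial, and resolution is poor: with a true ORR of 30%, the exact 95% CI would still contain 14% with probability 48% at a fixed n of 29.
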